8.2.8 Pharmacodynamic Assessments

[figure not shown]
Venous blood samples of approximately 3 mL will be collected for measurement of [REDACTED] at timepoints listed in the Schedule of Activities.

8.2.10 Antibody Testing Procedures

Blood sample(s) for antibody testing are to be collected according to the time points specified in the Schedule of Activities ([Table 1-1](#), [Table 1-3](#), [Table 1-5](#)) for the measurement of anti-AMG 330 binding antibodies and anti-pembrolizumab antibody (as necessary). Subjects testing positive for binding antibodies may be further characterized. Subjects who test positive for anti-AMG 330 antibodies at the final scheduled antibody time point and have clinical sequelae that are considered potentially related to an anti-AMG 330 antibody response will also be asked to return for additional follow-up testing. This testing is to occur approximately every 3 months from the last

antibody time point and continue until: (1) antibodies are no longer detectable; or (2) the subject has been followed for a period of at least 1 year (\pm 4 weeks) post administration of AMG 330. All follow-up results, both positive and negative will be communicated to the sites. More frequent testing or testing for a longer period of time may be requested in the event of safety-related concerns. Refer to the Schedule of Activities ([Table 1-1](#), [Table 1-3](#), [Table 1-5](#)), as applicable, for specific time points, and the laboratory manual for detailed collection and handling instructions.

Approved

Approved

9. Statistical Considerations

9.1 Statistical Hypotheses

This is a phase 1 study and no formal statistical hypothesis will be tested.

9.2 Sample Size Determination

Approximately 20 subjects will be enrolled in this study with at least 6 DLT evaluable subjects in each cohort. With 6 evaluable subjects in 1 cohort, there is an 82% chance of observing at least 1 DLT if the true DLT rate is 25%. For cohort 1, at least 10 subjects will be dosed through study day 28.

9.3 Analysis Sets, Subgroups, and Covariates

9.3.1 Analysis Sets

[figure not shown]
The analysis of all endpoints, unless noted otherwise, will be conducted on the Safety Analysis Set defined as all subjects that are enrolled and receive at least 1 dose of AMG 330 or pembrolizumab.

The analysis of DLT will be restricted to DLT-evaluable subjects (see definition of DLT-evaluable in [Section 6.2.1](#)).

The PK Analysis Set will contain all subjects who have received at least 1 dose of the AMG 330 or pembrolizumab and have at least 1 PK sample collected. These subjects will be evaluated for PK analysis unless the number of data points required for analysis is not enough, or significant protocol deviations have affected the data, or if key dosing or sampling information is missing.

9.3.2 Covariates

This phase 1 study has no prespecified covariates.

9.3.3 Subgroups

This phase 1 study has no prespecified subgroups.

9.3.4 Handling of Missing and Incomplete Data

Details on handling of missing and incomplete data are described in the statistical analysis plan.

9.4 Statistical Analyses

The statistical analysis plan will be developed and finalized before database lock.

Details of the statistical analysis will be described in the statistical analysis plan. Below is a summary of the timing and methods for the planned statistical analyses. To preserve study integrity, the final analysis will be conducted and reported following the end of study, as defined in [Section 4.4.1](#).

9.4.1 Planned Analyses

9.4.1.1 Interim Analysis and Early Stopping Guidelines

Safety data will be reviewed on an ongoing basis. A DLRM will occur when at least 10 treated subjects in cohort 1 have been dosed through study day 28 to determine if the safety profile of initial steps in cohort 1 is acceptable to begin enrollment of cohort 2 or if the study should be stopped. If 3 or more of the 10 treated subjects in cohort 1 experience a DLT by day 28, the guidance to the DLRT is to recommend not to initiate cohort 2. The stopping rule is based on having at least a posterior probability of > 70% that the DLT rate is > 20% assuming a prior distribution of Beta (0.40, 1.60). If the true DLT rate is 10%, 20%, 30%, 40%, or 50%, then the probability of stopping the study at the interim analysis is 7%, 32%, 62%, 83%, 95%, respectively.

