4.1 Overall Design

This is a phase 1b study assessing safety, tolerability, PK, pharmacodynamics, and efficacy of AMG 330 administered as clV infusion in combination with pembrolizumab in adult subjects with R/R AML.

The study is a non-randomized study and will consist of 2 sequential dosing cohorts. Both cohorts will include AMG 330 and pembrolizumab with the difference being the initiation date for pembrolizumab treatment.

This study will use a staggered enrollment approach. Subject enrollment will start with cohort 1 ([Section 4.1.1](#)). The first subject dosed in cohort 1 will serve as the sentinel subject. Subsequent subjects dosed in cohort 1 will start AMG 330 (█ µg/day) administration once sentinel subject has cleared the study day 21 dose (AMG 330 monotherapy at █ µg/day). Per sponsor determination, if the sentinel subject does not experience a dose-limiting toxicity (DLT) on days 15 to 21 after pembrolizumab is administered, the other subjects in cohort 1 will be allowed to continue the planned treatment schedule. If the sentinel subject experiences a DLT during days 15 to 21, the dose level review team (DLRT) will discuss the case and the decision will be made by the sponsor based on clinical assessments of the adverse event and potential decisions by the sponsor may include stopping AMG 330 and/or pembrolizumab, dose de-escalation of AMG 330, or continuing therapy at full dose. Investigators and sponsor will meet after all subjects in cohort 1 have completed study day 28 (ie, AMG 330 █ µg/day dose level in combination with pembrolizumab) to assess the safety profile. If pre-specified safety criteria are met (≤ 3 out of 10 treated subjects in cohort 1 experienced DLT by day 28), subjects enrolled in cohort 2 ([Section 4.1.2](#)) may proceed with the treatment schedule. Similar to cohort 1, the first subject dosed in cohort 2 will serve as the sentinel subject. Per sponsor determination, if the sentinel subject does not

experience a DLT during the first 7 days, the other subjects in cohort 2 will be allowed to continue the planned treatment schedule.

Safety data will be continuously monitored throughout the whole treatment period. Sponsor in consultation with investigators may reconvene to make appropriate safety measures and adjustments as needed.

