6.2 Dose Modification

6.2.1 Dose-cohort Study Escalation/De-escalation and Stopping Rules, Dose-Limiting Toxicities (DLTs)

Step Dose Level Determination

A decision to proceed with the next step dose of AMG 330 for each subject in cohorts 1 and 2 will be based on investigator's assessment of safety and upon approval by Sponsor.

In cohort 1, a sentinel subject will be treated first. The minimal interval between treatment start for the sentinel subject and other subjects in the cohort is 21 days. If the sentinel subject has not experienced a DLT by day 14 at █ µg/day AMG 330, he/she will proceed with 200 mg pembrolizumab on day 15 and remain at an AMG 330 dose level of █ µg/day for 7 days (until day 21). If the sentinel subject experiences a DLT during the first 7 days of treatment with AMG 330 at █ µg/day, this subject will be replaced, but the DLT will still be counted towards the study stopping rules. If the sentinel subject does not experience a DLT before or on day 21, the next subjects in the cohort may initiate dosing. If a sentinel subject experiences a DLT, the sponsor will issue a decision based on the evaluation of clinical significance of the adverse event by the DLRT and potential decisions by the sponsor may include stopping AMG 330 and/or pembrolizumab, dose de-escalation of AMG 330, or continuing therapy at full dose.

Cohort 2 will be initiated only after all subjects in cohort 1 completed study day 28 (ie, AMG 330 █ µg/day dose level in combination with pembrolizumab for 7 days), and if the rate of DLT is ≤ 3 out of 10 subjects. After receiving the DLRT recommendation, sponsor will render a final decision and will issue a written notification of the decision to investigators. Further information on dose level review meetings (DLRMs) is provided in [Section 11.3](#).

Individual Stopping Rules

Dosing for an individual will be stopped for any occurrence of a DLT. The event will be reviewed by the investigator and Sponsor for evidence of relationship to treatment and

clinical or medical significance to decide whether dosing may be resumed for the individual and any modifications to the dosing, if appropriate.

Dose Limiting Toxicities

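### At exactly 3 DLTs in 10 cohort 1 subjects, the design sections let cohort 2 open and the stopping rule says not to open it

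*Protocol*

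**What the plan says.** Five places deal with the same decision, which is whether cohort 2 opens given the number of cohort 1 subjects with a DLT out of 10 at the day 28 review.

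Three of them accept 3 DLTs:

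- Protocol 4.1 gives the safety criterion for cohort 2 as "≤ 3 out of 10 treated subjects in cohort 1 experienced DLT by day 28". SAP 3.1 repeats it.
- Protocol 6.2.1, which covers escalation and stopping rules, makes the start of cohort 2 conditional on all cohort 1 subjects completing day 28 "if the rate of DLT is ≤ 3 out of 10 subjects".

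Two of them treat 3 DLTs as a stop:

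- Protocol 9.4.1.1 says: "If 3 or more of the 10 treated subjects in cohort 1 experience a DLT by day 28", and then "the guidance to the DLRT is to recommend not to initiate cohort 2". SAP 7.1 repeats it.

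The last two sections also give the basis of the rule: a Beta(0.40, 1.60) prior and a posterior probability above 70% that the DLT rate exceeds 20%. They print stopping probabilities of 7, 32, 62, 83 and 95% for true DLT rates of 10, 20, 30, 40 and 50%.

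The synopsis gives no number, and SAP section 10 reports no changes from the protocol.

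**The concern.** At 0 to 2 DLTs the two rules agree that cohort 2 may open, and at 4 or more they agree that it should not. At exactly 3 they disagree, and nothing in either document says which takes precedence.

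This is the only numerical rule for opening cohort 2, in which subjects start both drugs on day 1. Protocol 2.3 itself warns that PD-1 blockade may worsen cytokine release syndrome, and Protocol 2.2.2.3 says that no combination toxicology study was done. If the design-section wording were followed, the trial would run on a looser safety boundary than the one whose operating characteristics the plan reports.

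**Working it through.** **Inputs.** From Protocol 9.4.1.1 and SAP 7.1: n = 10; prior Beta(0.40, 1.60); stop if P(DLT rate > 0.20 | data) > 0.70; stopping probabilities as printed. From Protocol 4.1, Protocol 6.2.1 and SAP 3.1: go at 3 or fewer of 10, which means stop at 4 or more.

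**Step 1: reproduce the printed stopping probabilities.** With X ~ Binomial(10, p), the chance of stopping is P(X ≥ 3) under the stopping rule and P(X ≥ 4) under the design-section rule. The difference between them is P(X = 3) = 120 p³(1 − p)⁷.

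| True DLT rate | Printed | P(X ≥ 3) | P(X ≥ 4) | P(X = 3) |
|---|---|---|---|---|
| 10% | 7% | 7.0% | 1.3% | 5.7% |
| 20% | 32% | 32.2% | 12.1% | 20.1% |
| 30% | 62% | 61.7% | 35.0% | 26.7% |
| 40% | 83% | 83.3% | 61.8% | 21.5% |
| 50% | 95% | 94.5% | 82.8% | 11.7% |

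All five printed values match stopping at 3 or more. The 50% entry is 0.9453 before rounding, hence 95%. None of the five matches stopping at 4 or more.

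**Step 2: find where the Bayesian criterion is first met.** After x DLTs in 10 the posterior is Beta(0.40 + x, 1.60 + 10 − x).

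| DLTs in 10 | Posterior | P(DLT rate > 20%) | Above 70%? |
|---|---|---|---|
| 2 | Beta(2.4, 9.6) | 0.4418 | No |
| 3 | Beta(3.4, 8.6) | 0.7195 | Yes |
| 4 | Beta(4.4, 7.6) | 0.8951 | Yes |

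The criterion is first met at 3.

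**Step 3: compare.** The prior, the threshold, the boundary of 3 and the stopping probabilities in the statistical section all agree with one another. Only the wording that accepts 3 of 10 departs from them. The last column of the first table is both the chance of reaching the disputed result and the stopping probability lost by following the looser wording. At a true rate of 30%, that loss takes the chance of stopping from 62% to 35%.

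**The case against.** The strongest reply is that no section compels cohort 2 to open at 3 DLTs. Protocol 4.1 and SAP 3.1 are permissive, Protocol 6.2.1 can be read as a necessary condition only, and 9.4.1.1 is guidance to the review team. A team that declined to open at 3 would breach none of them. Protocol Appendix 3 (11.3) also requires a unanimous vote to go on to cohort 2, and under Protocol 6.2.1 the sponsor makes the final decision. Both cohorts have sentinel subjects as well, so this is not the study's only safety check.

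These points are accurate, and they lower the chance that the looser text alone would open cohort 2. They do not settle what the pre-specified rule is. At 3 DLTs one voting member can cite 6.2.1 to show the criterion is met, and another can cite 9.4.1.1 to show it is not.

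It is also fair to say that the printed stopping probabilities are correct for the rule printed beside them. They become wrong only if the design-section wording governs.

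A further point concerns the denominator. The review is triggered on a minimum: "A DLRM will occur when at least 10 treated subjects in cohort 1 have been dosed through study day 28". With 3 DLTs the posterior is 0.664 at n = 11 and 0.608 at n = 12, both below 70%, so at those sizes the criterion is first met at 4 (0.860 and 0.821). The boundary of 3 is therefore exact only at n = 10. This is a separate gap and does not reconcile the two texts, which both state their rule for 10 subjects.

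**Conclusion.** The contradiction is real, and the text is wrong as written. At 3 of 10 the design sections treat the safety criterion as met, while the stopping rule calls for a recommendation not to open cohort 2. The stated prior, threshold and operating characteristics all support the stopping rule, so the likely error is in Protocol 4.1, Protocol 6.2.1 and SAP 3.1.

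If the looser wording were followed, the chance of stopping would fall by 6 to 27 percentage points across the true DLT rates the plan considers, with the largest fall at 30%. The error is in the less safe direction. These figures assume exactly 10 subjects at the review and independent DLTs with a common rate, which is the binomial model behind the plan's own numbers. The rule should be settled before the dose level review meeting.

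**What to change.** State one rule in all five places.

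- **If the stated criterion and operating characteristics are kept (preferred):** change the limit from at most 3 of 10 to at most 2 of 10 in Protocol 4.1, Protocol 6.2.1 and SAP 3.1. Protocol 9.4.1.1 and SAP 7.1 stay as they are at n = 10.
- **If the sponsor intends to allow 3 of 10:** change the stopping boundary in Protocol 9.4.1.1 and SAP 7.1 to 4 or more, and replace the stopping probabilities with 1, 12, 35, 62 and 83%. The posterior threshold must also be raised. With this prior and n = 10, any cutoff from 0.7195 up to just under 0.8951 stops first at 4. The sponsor should justify the looser boundary.

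In the same revision, it would help to say what applies if more than 10 subjects have reached day 28. One option is to base the rule on the first 10; another is to tabulate the boundary by n from the posterior criterion.

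The preferred change is one digit in three places. It adds no subjects and needs no new calculation at n = 10. It does require a SAP correction and a protocol amendment, with ethics committee submission and, where necessary, approval as set out in Protocol Appendix 3.

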9.4.1.2 Primary Analysis

The primary analysis will occur when all subjects complete end of study.

9.4.1.3 Final Analysis

The primary analysis will also be the final analysis.

9.4.2 Methods of Analyses

9.4.2.1 General Considerations

Descriptive statistics will be provided for selected demographics, safety, PK, [REDACTED] and [REDACTED] data overall and by cohort and time as appropriate.

Descriptive statistics on continuous data will include means, medians, standard deviations and ranges, while categorical data will be summarized using frequency counts and percentages. Graphical summaries of the data may also be presented.

Confidence intervals (CI) for proportions will be estimated using an exact method proposed by [Clopper and Pearson \(1934\)](#).

9.4.2.2 Efficacy Analyses

Endpoint	Statistical Analysis Methods
Primary	Not applicable
Secondary	The proportion of subjects with a response to treatment (CR _{MRD} -, CR, CRi, MLFS, or CRh*) and exact 80% CI will be tabulated overall by cohort. Duration of response will be presented per subject and Kaplan-Meier estimates may also be further presented if data allows.
Exploratory	Details will be provided in the statistical analysis plan

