
 Evaluate the anti-leukemia activity of AMG 330 administered in combination with pembrolizumab in R/R AML patients 	
 Responses to treatment with AMG 330 administered in combination with pembrolizumab. Response is defined as any of the following: complete remission without minimum residual disease (CR_{MRD}), complete remission (CR), CR with incomplete recovery (CRI), or morphological leukemia-free state (MLFS), or partial remission (all according to the 2017 European LeukemiaNet (ELN) criteria (Döhner et al, 2017)). Duration of response

 Evaluate the pharmacokinetics (PK) of AMG 330 when AMG 330 and pembrolizumab are administered in combination 	
 Descriptive statistics of AMG 330 concentrations and PK parameters.

 Evaluate the immunogenicity of AMG 330 when administered in combination with pembrolizumab 	
 Incidence of anti-AMG 330 antibody formation

Exploratory	

 Evaluate the pharmacokinetics (PK) of pembrolizumab when AMG 330 and pembrolizumab are administered in combination 	
 Descriptive statistics of pembrolizumab concentrations.

 Evaluate the immunogenicity of pembrolizumab when AMG 330 and pembrolizumab are administered in combination 	
 Incidence of anti-pembrolizumab antibody formation

Approved

• Evaluate the relationship between AMG 330 and pembrolizumab exposure and response to treatment	
• Correlate the serum levels AMG 330 and pembrolizumab with changes in tumor burden (exposure/efficacy) and with adverse event incidence (exposure/safety)
--	--

4. Study Design

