As of the 17 June 2019 data snapshot date, 5 of 39 evaluable subjects had a response. One subject (cohort 11 [REDACTED] µg/day) achieved CR, 3 subjects (1 each in cohort 8 [REDACTED] µg/day], cohort 9 [REDACTED] µg/day], and cohort 12 [REDACTED] µg/day]) achieved CRI, and 1 subject (cohort 2 [REDACTED] µg/day]) achieved morphologic leukemia-free state (MLFS). The objective response rate based on subjects who achieved either a CR, CRI, CR with partial hematologic recovery (CRh), partial remission (PR), or MLFS was 12.8% (80% CI: 6.4%, 22.5%). Two additional subjects in cohort 15 ([REDACTED] µg/day) achieved CR (1 subject) and CRI (1 subject) after the data snapshot date of 17 June 2019.

Refer to the [AMG 330 Investigational Brochure](#) for further information.

Justification for Pembrolizumab Dose

The planned dose of pembrolizumab for this study is 200 mg every 3 weeks (Q3W). Based on the totality of data generated in the Keytruda development program, 200 mg Q3W is the appropriate dose of pembrolizumab for adults across all indications and regardless of tumor type. As outlined below, this dose is justified by:

- Clinical data from 8 randomized studies demonstrating flat dose and exposure-efficacy relationships from 2 mg/kg Q3W to 10 mg/kg every 2 weeks (Q2W),
- Clinical data showing meaningful improvement in benefit-risk including overall survival at 200 mg Q3W across multiple indications, and
- Pharmacology data showing full target saturation in both systemic circulation (inferred from pharmacokinetic [PK] data) and tumor (inferred from physiologically-based PK analysis) at 200 mg Q3W.

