The planned length of an AMG 330 infusion-free interval between cycles is 1 week (+3 days if needed for logistical reasons). The duration can be extended up to 4 weeks after consultation with the sponsor for subjects who achieved a response (CR, CRh, CRi, or MLFS) with no detectable blasts in bone marrow at the end of infusion. Weekly hematology assessments should be performed to confirm recovery of peripheral blood counts. Once peripheral blood counts have returned to baseline levels, the next treatment cycle can be initiated.

In subjects who achieved a response with no detectable blasts in bone marrow at end of infusion, the infusion-free interval may also be extended up to a maximum of 6 weeks in case of insufficient recovery of peripheral blood counts (neutrophils < 500/ μ L, platelets < 20 000/ μ L without transfusion) and after consultation with the sponsor. In case the infusion-free interval is extended to 4-6 weeks, a bone marrow assessment is recommended 4 weeks after the end of the infusion cycle. In case this assessment shows detectable leukemic infiltration of the bone marrow, treatment should be resumed immediately even if peripheral blood counts have not yet recovered at this time point.

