- Hematological or extramedullary relapse subsequent to CR/CRh*/CRI/MLFS on protocol treatment. Exception: a blast count > 5% at the pre-dose assessment (after the infusion-free interval) would not lead to permanent treatment discontinuation even if the count had been < 5% directly after the previous treatment cycle.
- An infusion interruption of more than 21 days due to an adverse event not clearly related to the underlying disease.

- Occurrence of CNS-related adverse event considered related to AMG 330 by the investigator and meeting 1 or more of the following criteria:
 - More than 1 seizure
 - A CNS-related adverse event CTCAE grade 4
 - A CNS-related adverse event leading to treatment interruption that needed more than 1 week to resolve to CTCAE grade ≤ 1
- Non-manageable GVHD
- Investigator's decision that a change of therapy is in the subject's best interest
- Administration of relevant non-permitted concomitant medications

Women who become pregnant while on study through 1 week after receiving the last dose of study drug will not receive subsequent scheduled doses and will be followed for safety until the end of study visit.

Men with pregnant partners or whose partners become pregnant while the subject is on study will receive subsequent scheduled doses and must practice sexual abstinence or use a condom while on study through 120 days after receiving the last dose of study drug.

All reasons for treatment discontinuation should be clearly and concisely documented in the eCRF. If a subject has not continued to present for study visits, the investigator should determine the reason and circumstances as completely and accurately as possible.

In any case of premature treatment discontinuation, the investigator should make every effort to perform all examinations scheduled for the end of treatment and safety follow-up visits. These data should be recorded, as they comprise an essential evaluation that should be performed prior to discharging any subject from the study and to allow for the evaluation of the study endpoints.

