11.1 Appendix 1. List of Abbreviations and Definitions of Terms

Abbreviation or Term	Definition/Explanation
AE	adverse event
ALT	alanine aminotransferase
AML	acute myeloid leukemia
APML	promyelocytic leukemia
AST	aspartate aminotransferase
BCG	Bacillus Calmette–Guérin
BiTE	bispecific T-cell engager
CAR	chimeric antigen receptor
CD	cluster of differentiation
CI	confidence interval
cIV	continuous intravenous
CL	clearance
CNS	central nervous system
CR	complete remission
CRF	case report form
CRh	complete remission with partial hematologic recovery
CRI	complete remission with incomplete count recovery
CRMRD-	complete remission without minimum residual disease
CRS	cytokine release syndrome
CTLA-4	cytotoxic T-lymphocyte-associated protein 4
CTCAE	Common Terminology Criteria for Adverse Events
DILI	drug-induced liver injury
DLRM	dose level review meeting
DLRT	dose level review team
DLT	dose-limiting toxicity
ECG	electrocardiogram
ECI	Events of Clinical Interest
ECOG	Easter Cooperative Oncology Group
eCRF	electronic case report form
EDC	electronic data capture
ELN	European LeukemiaNet
EOI	end of infusion
EOT	end of treatment
FDA	Food and Drug Administration
GCP	Good Clinical Practice

GLP	Good Laboratory Practice
GSO	Global Safety Officer
GVHD	Graft versus Host Disease
HBsAg	hepatitis B surface antigen
HBV	hepatitis B virus
HCV	hepatitis C virus
HIV	human immunodeficiency virus
HNSTD	highest non-severely toxic dose
HRT	hormonal replacement therapy
HSCT	hematopoietic stem cell transplantation
ICF	informed consent form
ICH	International Council for Harmonisation
IEC	Independent Ethics Committee
IFN	interferon
Ig	immunoglobulin
IL	interleukin
IND	Investigational New Drug
INR	international normalized ratio
IPIM	Investigational Product Instruction Manual
IRB	Institutional Review Board
IRT	interactive response technology that is linked to a central computer in real time as an interface to collect and process information
IUD	intrauterine device
IV	intravenous
IVSS	intravenous solution stabilizer
LDH	lactate dehydrogenase
MLFS	morphologic leukemia-free state
MTD	maximum tolerated dose
NCT	National Clinical Trials
NOD	non-obese diabetic
PCR	polymerase chain reaction
PD-1	programmed cell death receptor
PD-L1/PD-L2	programmed cell death ligand 1/2
PK	pharmacokinetic
PR	partial remission

Approved

R/R AML	relapsed or refractory AML
RBC	red blood cell
SAP	Statistical Analysis Plan
SC	subcutaneous
SCID	severe combined immunodeficiency
SFU	safety follow-up

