### 5.5 Treatment Response

Treatment response is defined in Appendix D. The data will be recorded on Disease Response CRF page.

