### 9.5.2 Analyses of Secondary Efficacy Endpoint(s)

The percentage of subjects with a response (CRMRD-, CR, CRi, MLFS, or PR) to treatment using the European Leukemia Net (ELN) Response Criteria in Acute Myeloid Leukemia (AML) (2017) will be summarized with an exact 80% confidence interval (CI) overall and by cohort. It will be presented using an exact method proposed by Clopper and Pearson (1934). Subjects missing post baseline disease assessments will be considered not to have achieved response.

Protocol Number: 20170646

**Date:** 25 August 2020 Page 21 of 35

Duration of response will be presented per subject and Kaplan-Meier (KM) estimates may be presented.

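### Could a remission recorded as CRh drop out of the response rate because the SAP has no CRh category?

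*Protocol*

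**What the plan says.** The response list in Protocol Section 9.4.2.2 ends with "MLFS, or CRh*) and exact 80% CI will be tabulated overall by cohort". It names CRi and CRh* separately and leaves out PR.

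The endpoint definition in Protocol Section 3 has no CRh and ends with "or partial remission (all according to the 2017 European LeukemiaNet (ELN) criteria". The synopsis agrees with Section 3. So does the SAP: Section 9.5.2 closes its list with "MLFS, or PR) to treatment using the European Leukemia Net (ELN) Response Criteria", and the endpoint table (Section 2.1) and the duration-of-response definition (Section 5.4) name the same five categories.

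CRh also appears elsewhere in the protocol:
- Section 6.1.1.1.1, on the infusion-free interval: "for subjects who achieved a response (CR, CRh, CRi, or MLFS".
- Section 6.2.2.1, on permanent discontinuation: "Hematological or extramedullary relapse subsequent to CR/CRh*/CRI/MLFS on protocol treatment".
- Section 4.3, on the phase 1a response rate: "CR with partial hematologic recovery (CRh), partial remission (PR), or MLFS was 12.8" percent.
- Appendix 1, where it is spelled out as "complete remission with partial hematologic recovery". No neutrophil or platelet thresholds are given.

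SAP Section 5.5 takes the definition of response from Appendix D, the 2017 ELN table, and adds: "The data will be recorded on Disease Response CRF page". SAP Section 10 declares no changes from the protocol's analyses.

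**The concern.** An investigator working from this protocol meets CRh several times as if it were a usable response label. The analysis plan never mentions it: not in the abbreviations, the response list, the duration-of-response definition or the ELN table. If the Disease Response CRF page accepts CRh, such a record matches none of the SAP's five categories. It could then be left out of the numerator and of duration of response, although Protocol Section 9.4.2.2 counts it. Someone would have to settle that subject's status in an open-label study with the data already in view. With about 20 subjects, one reclassified responder moves the rate visibly. The no-changes statement in SAP Section 10 adds to the unease, since it does not hold against Section 9.4.2.2.

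**Working it through.** **1. The protocol's own figure.** The exact (Clopper-Pearson) 80% interval has lower limit Beta⁻¹(0.10; x, n − x + 1) and upper limit Beta⁻¹(0.90; x + 1, n − x). For the phase 1a data in Protocol Section 4.3, x = 5 and n = 39. This gives 5/39 = 12.8% with limits 6.4% and 22.5%, as printed there.

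**2. The response lists side by side.**

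| Place | CRh | PR |
|---|---|---|
| Protocol Section 3 and synopsis | no | yes |
| Protocol Section 9.4.2.2 | yes (CRh*) | no |
| Protocol Section 11.11 (ELN table) | no | yes |
| SAP Sections 2.1, 5.4, 9.5.2 | no | yes |
| SAP Appendix D (ELN table) | no | yes |

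Among the places that define or analyse this trial's endpoint, Section 9.4.2.2 stands alone. Sections 6.1.1.1.1 and 6.2.2.1 are management rules, and Section 4.3 reports another study.

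**3. How a CRh remission is classified under the plan.** Protocol Section 8.2.2.1 and SAP Sections 5.5 and 9.5.2 all send the classification to the 2017 ELN criteria. Neither document gives thresholds for CRh, so I take it by its name: a complete remission in which blood counts have recovered only in part. Appendix D then leaves these possibilities:
- Neutrophils at least 1000/µL and platelets at least 100 000/µL: CR.
- One of the two below its threshold, all other CR criteria met: CRi.
- Both below: CRi if the table's wording is read inclusively. If not, MLFS, which asks for marrow blasts under 5%, no Auer-rod blasts and no extramedullary disease, and requires no recovery of counts.

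Each of these is a response in SAP Section 9.5.2. Each also enters duration of response in Section 5.4, whose formula uses the date of first response and the date of progression or death, not the response label. The numerator is the same whether the site writes CRh or the ELN category.

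**4. Size if Appendix D were ignored.** Each CRh record dropped lowers the rate by 1/N. The responder counts here are assumptions, chosen only to show scale:
- N = 20: 2/20 = 10.0% (2.7% to 24.5%) against 3/20 = 15.0% (5.6% to 30.4%), a shift of 1/20 = 5 points.
- N = 10: 1/10 = 10.0% (1.0% to 33.7%) against 2/10 = 20.0% (5.5% to 45.0%), a shift of 1/10 = 10 points.
- No CRh record: no shift at any N.

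The minimum of 6 per cohort refers to DLT-evaluable subjects. Response is analysed on the Safety Analysis Set, so 6 is not a planned denominator for it.

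**5. How often the label might arise.** The phase 1a response definition in Section 4.3 did allow CRh. Its five responders were 1 CR, 3 CRi and 1 MLFS, and the two later ones were 1 CR and 1 CRi. None of the 5 + 2 = 7 was CRh.

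**The case for a change.** The best argument for acting is that the mapping from CRh to CRi or MLFS is my inference. Neither document defines CRh, explains the asterisk or states the mapping, and a single SAP sentence would settle it before any data are seen. The same sentence could correct SAP Section 10, whose statement is inaccurate against Section 9.4.2.2 whether or not CRh is ever recorded: the SAP drops CRh* and adds PR.

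Part of this stands. The two protocol lists do conflict, and Section 10 does not say which one the SAP follows. The CRF page was not available to me, and the text of SAP Appendix A is not shown. SAP Section 8.3 cites that appendix for imputing dates, so a CRh rule there is unlikely but cannot be excluded.

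The consequence does not stand. A sentence assigning CRh to CRi or MLFS by the Appendix D criteria would repeat what SAP Section 5.5 already directs. PR is the one list difference that no other category absorbs. The SAP settles it by including PR in all three of its response lists, in line with the protocol's endpoint definition.

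**Conclusion.** No change is needed. The mismatch is a clerical slip in Protocol Section 9.4.2.2, and the SAP has already resolved it by following the protocol's endpoint definition. The SAP as written gives a sound response rate and duration of response, with an expected effect of zero. A loss of 5 points overall, or 10 in a cohort of 10, needs three things together: a CRF page that offers CRh, a subject recorded that way, and an analyst who counts labels without applying Appendix D. The endpoint is secondary and descriptive, no hypothesis is tested, and the decision on opening cohort 2 rests on DLTs, so no conclusion of the trial depends on this point.

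This rests on two assumptions: that CRh means what its spelled-out name says, and that response is classified by the ELN criteria as SAP Section 5.5 states. Section 9.4.2.2 can be tidied whenever the protocol is next amended for another reason, but no result depends on it.
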